Clinical Trial Protocol

Document Number: c13723133-03

EudraCT No.: 2016-004862-24

BI Trial No.: 1346-0018

BI Investigational Product: BI 425809

Title: Effects of rifampicin on the pharmacokinetics of BI 425809 following oral administration in healthy male subjects (an open-label, two-period, fixed-sequence trial)

Clinical Phase: I

Trial Clinical Monitor:

Phone: [REDACTED]

Fax: [REDACTED]

Principal Investigator:

Phone: [REDACTED]

Fax: [REDACTED]

Status: Final Protocol (Revised Protocol (based on global amendment 2))

Version and Date: Version: 3.0 Date: 05 Apr 2017

Page 1 of 61

Proprietary confidential information

© 2017 Boehringer Ingelheim International GmbH or one or more of its affiliated companies. All rights reserved.
This document may not - in full or in part - be passed on, reproduced, published or otherwise used without prior written permission

Proprietary confidential information © 2017 Boehringer Ingelheim International GmbH or one or more of its affiliated companies

CLINICAL TRIAL PROTOCOL SYNOPSIS

Name of company: Boehringer Ingelheim		Tabulated Trial Protocol			
Name of finished product: Not applicable					
Name of active ingredient: BI 425809					
Protocol date: 20 December 2016	Trial number: 1346-0018		Revision date: 05 April 2017		
Title of trial: Effects of rifampicin on the pharmacokinetics of BI 425809 following oral administration in healthy male subjects (an open-label, two-period, fixed-sequence trial)					
Principal Investigator: [REDACTED]					
Trial site: [REDACTED]					
Clinical phase:	I				
Objective:	To investigate whether and to what extent co-administration of multiple doses of rifampicin affect single dose pharmacokinetics of BI 425809 in healthy male subjects and to characterize the single dose pharmacokinetics of the metabolite BI 761036				
Methodology:	Open-label, fixed-sequence trial with 2 treatments (A and B)				
No. of subjects:					
total entered:	16				
each treatment:	16				
Diagnosis:	Not applicable				
Main criteria for inclusion:	Healthy male subjects, age of 18 to 55 years, body mass index (BMI) of 18.5 to 29.9 kg/m ²				
Trial product 1:	BI 425809, 25 mg tablet				
dose:	25 mg as single dose in treatments A and B				
mode of admin.:	Oral administration with 240 mL of water after overnight fast				
Trial product 2:	Eremfat® 600 mg tablet (1 tablet containing 600 mg rifampicin)				
dose:	600 mg once daily (qd) for 10 days in treatment A				
mode of admin.:	Oral administration with 240 mL of water				
Duration of treatment:	Treatment B, Reference (BI 425809 alone): Single dose of 25 mg BI 425809 on Day 1 Treatment A, Test (rifampicin + BI 425809): 10 days of rifampicin (600 mg qd) treatment combined with a single dose of 25 mg BI 425809 on the seventh day of the rifampicin treatment. BI 425809 single doses in treatments B and A will be separated by a wash-out period of at least 49 days.				

Proprietary confidential information © 2017 Boehringer Ingelheim International GmbH or one or more of its affiliated companies

Name of company: Boehringer Ingelheim		Tabulated Trial Protocol		
Name of finished product: Not applicable				
Name of active ingredient: BI 425809				
Protocol date: 20 December 2016	Trial number: 1346-0018		Revision date: 05 April 2017	
Criteria for pharmacokinetics: Primary endpoints: AUC_{0-168} and C_{max} of BI 425809 in plasma Secondary endpoints: $AUC_{0-\infty}$ of BI 425809 in plasma, $t_{1/2}$ of metabolite BI 761036 in plasma [REDACTED]				
Criteria for safety: Adverse events (AEs) including clinically relevant findings from the physical examination, safety laboratory tests, 12-lead electrocardiogram (ECG), vital signs (blood pressure [BP], pulse rate [PR])				
Statistical methods: Relative bioavailability will be estimated based on the point estimators of the intra-subject ratio (test to reference treatments) of the geometric means (gMeans) of the primary endpoints and the secondary endpoint $AUC_{0-\infty}$ of BI 425809 in plasma. Additionally their corresponding two-sided 90% confidence intervals will be provided. The statistical model will be a (mixed effects) ANOVA on log transformed parameters, including effects for 'subjects' and 'treatment'. Confidence intervals will be based on the residual error from the ANOVA. Descriptive statistics will be calculated for all endpoints.				

Proprietary confidential information © 2017 Boehringer Ingelheim International GmbH or one or more of its affiliated companies

FLOW CHART

Period	Visit	Day	Planned time (relative to first drug administration [h:min])	Approximate clock time of actual day [h:min]	Event and comment	Safety laboratory	PK plasma (BI 425809)	PK plasma (metabolites)	Urine for 6 β -OH cortisol	12-lead ECG	Vital signs (BP, PR)	Questioning for AEs and concomitant therapy ⁶
SCR	1	-21 to -1			Screening (SCR) ¹	x				x	x	
Treatment B, Reference (BI 425809 single dose)	2	1	-2:00	06:00	Admission to trial site ² , allocation to study subject numbers	x ^{5,2}	x ²	x ²	x ²		x ²	x ²
			0:00	08:00	Drug administration BI 425809							
			0:30	08:30		x						
			1:00	09:00		x						
			1:30	09:30		x						
			2:00	10:00	240 mL fluid intake	x						
			2:30	10:30		x						
			3:00	11:00		x	x					
			3:30	11:30		x						
			4:00	12:00	240 mL fluid intake	x					x	
			4:30	12:30		x						
			5:00	13:00	Lunch ³	x						
			6:00	14:00		x	x					
			8:00	16:00		x						
			10:00	18:00		x						
			11:00	19:00	Dinner							
			12:00	20:00		x	x				x	
			2	24:00	08:00 Breakfast (voluntary) ³ , discharge	x	x			x	x	
				34:00	18:00 Ambulatory visit	x	x				x	
			3	48:00	08:00 Ambulatory visit	x	x				x	
			4	72:00	08:00 Ambulatory visit	x	x				x	
			5	96:00	08:00 Ambulatory visit	x	x				x	
			8	168:00	08:00 Ambulatory visit	x ⁷	x ⁷				x ⁷	
			10	216:00	08:00 Ambulatory visit	x ⁷	x ⁷				x ⁷	
			12	264:00	08:00 Ambulatory visit	x ⁷	x ⁷				x ⁷	
			15	336:00	08:00 Ambulatory visit	x ⁷	x ⁷	x ⁷			x ⁷	
			18	408:00	08:00 Ambulatory visit	x ⁷	x ⁷				x ⁷	
			22	504:00	08:00 Ambulatory visit	x ⁷	x ⁷				x ⁷	
			25	576:00	08:00 Ambulatory visit	x ⁷					x ⁷	
			29	672:00	08:00 Ambulatory visit	x ⁷					x ⁷	
			32	744:00	08:00 Ambulatory visit	x ⁷					x ⁷	
			36	840:00	08:00 Ambulatory visit	x ⁷					x ⁷	
			43	1008:00	08:00 Ambulatory visit	x ⁷	x ⁷				x ⁷	

Proprietary confidential information © 2017 Boehringer Ingelheim International GmbH or one or more of its affiliated companies

FLOW CHART (cont.)

Period	Visit	Day	Planned time (relative to BI 425809 administration) [h:min]	Approximate clock time of actual day [h:min]	Event and comment	Safety laboratory	PK plasma (BI 425809)	PK plasma (metabolites)	Urine for 6β-OH cortisol	12-lead ECG	Vital signs (BP,PR)	Questioning for AEs and concomitant therapy ⁶
Treatment A - Test (Rifampicin multiple dose + BI 425809 single dose)	3	-6	-134:30	17:30	Admission to trial site ²	x ^{2,8}						x ²
			-134:00	18:00	Rifampicin administration							
			-133:00	19:00	Dinner							
			-132:00	20:00	Discharge from trial site							x
		-5	-110:00	18:00	Ambulatory visit, rifampicin administration							x
			-86:00	18:00	Ambulatory visit, rifampicin administration							x
		-3	-72:00	08:00	Ambulatory visit	x ⁷						x ⁷
			-62:00	18:00	Ambulatory visit, rifampicin administration							x
		-2	-38:00	18:00	Ambulatory visit, rifampicin administration							x
			-14:00	18:00	Ambulatory visit, rifampicin administration							x
		1	-2:00	06:00	Admission to trial site ²	x ²	x ²	x ²	x ²	x ²	x ²	x ²
			0:00	08:00	Drug administration BI 425809							
			0:30	08:30		x						
			1:00	09:00		x						
			1:30	09:30		x						
			2:00	10:00	240 mL fluid intake	x						
			2:30	10:30		x						
			3:00	11:00		x	x					
			3:30	11:30		x						
			4:00	12:00	240 mL fluid intake	x						x
			4:30	12:30		x						
			5:00	13:00	Lunch ³	x						
			6:00	14:00		x	x					
			8:00	16:00		x						
			10:00	18:00	Rifampicin administration ³	x						x
			11:00	19:00	Dinner							
			12:00	20:00		x	x					x
		2	24:00	08:00	Breakfast (voluntary), discharge	x	x			x	x	
			34:00	18:00	Ambulatory visit, rifampicin administration ³	x	x					x
		3	48:00	08:00	Ambulatory visit	x	x					x
			58:00	18:00	Ambulatory visit, rifampicin administration							
		4	72:00	08:00	Ambulatory visit	x	x	x				x
			82:00	18:00	Ambulatory visit, rifampicin administration							x
		5	96:00	08:00	Ambulatory visit	x	x					x
			168:00	08:00	Ambulatory visit	x ⁷	x ⁷					x ⁷
EOT	4	12 to 23			End of trial (EOT) examination ⁴	x				x	x	x

1. Subject must be informed and written informed consent obtained prior to starting any screening procedures. Screening procedures include physical examination, check of vital signs, ECG, safety laboratory (including drug screening), demographics (including determination of body height and weight, smoking status and alcohol history), relevant medical history, concomitant therapy and review of inclusion/exclusion criteria. Pharmacogenetic samples will be collected if needed.
2. The time is approximate; the procedure is to be performed and completed within 3 h prior to drug administration.
3. If several actions are indicated at the same time point, this will be the last action.
4. End of trial examination includes physical examination, vital signs, ECG, safety laboratory, recording of AEs and concomitant therapies.
5. Including urine drug screening and alcohol breath test.

Proprietary confidential information © 2017 Boehringer Ingelheim International GmbH or one or more of its affiliated companies

6. AEs and concomitant therapies will be recorded throughout the trial, but will be specifically asked for at the time points indicated in the [Flow Chart](#) above.
7. The time is approximate; the procedure is to be performed and completed within ± 3 h of planned time.
8. Urine drug screen and alcohol breath test only.

TABLE OF CONTENTS

TITLE PAGE	1

gCV	Geometric coefficient of variation
GlyT1	Glycine Transporter 1
gMean	Geometric mean
(HP)LC-MS/MS	(High performance) liquid chromatography with tandem mass spectrometry
IEC	Independent Ethics Committee
IRB	Institutional Review Board

Proprietary confidential information © 2017 Boehringer Ingelheim International GmbH or one or more of its affiliated companies

ISF	Investigator site file
	[REDACTED]
	[REDACTED]
NC	Not calculated
NMDA	N-methyl-D-aspartate
NOA	Not analysed
NOAEL	No observed adverse effect level
NOP	No peak detectable
NOR	No valid result
NOS	No sample available
PK	Pharmacokinetic(s)
PKS	PK analysis set
PR	Pulse rate
qd	Quaque die , once daily
QT	Time between start of the Q-wave and the end of the T-wave in an electrocardiogram
R	Reference (product or treatment)
REP	Residual effect period
RPM	Report planning meeting
SAE	Serious adverse event
SCR	Screening
SPC	Summary of product characteristics
T	Test (product or treatment)
	[REDACTED]
	[REDACTED]
	[REDACTED]
TS	Treated set
TSAP	Trial statistical analysis plan
ULN	Upper limit of normal
	[REDACTED]

A large black rectangular redaction box covers the majority of the page content, from approximately y=113 to y=886. The redaction is irregular, with jagged edges and some white space visible at the top and bottom. There are also small black rectangular redaction marks at the very top and bottom left corners of the page.

Proprietary confidential information © 2017 Boehringer Ingelheim International GmbH or one or more of its affiliated companies

[REDACTED]

[REDACTED]

[REDACTED]

[REDACTED]

[REDACTED]

A series of nine horizontal black bars of varying lengths, decreasing from left to right, set against a white background. The bars are positioned in a staggered, non-linear fashion, creating a sense of depth or a stepped pattern. The lengths of the bars decrease from approximately 80 pixels on the far left to about 20 pixels on the far right. The bars are solid black and have no texture or shading.

Proprietary confidential information © 2017 Boehringer Ingelheim International GmbH or one or more of its affiliated companies

[REDACTED]

[REDACTED]

3. DESCRIPTION OF DESIGN AND TRIAL POPULATION

3.1 OVERALL TRIAL DESIGN AND PLAN

This clinical phase I study will be done as an open-label, two period, fixed-sequence trial with 2 treatments in order to compare the test treatment (A) to the reference treatment (B) in a single centre.

The trial will consist of 4 visits. Visit 1 will be the screening investigation.

Each subject will receive treatment B (reference) in Visit 2 and treatment A (test) in Visit 3. The two treatments are described below. The administrations of the single dose of BI 425809 in the first period (Visit 2) and in the following combined treatment period (Visit 3) will be separated by a wash-out period of at least 49 days. For details refer to [Section 4.1](#).

Visit 4 will be the end-of-trial examination.

Reference treatment (BI 425809 alone):

One tablet of 25 mg BI 425809 will be given as a single dose on Day 1 of Visit 2 (treatment B).

Test treatment (rifampicin + BI 425809):

During the second period of the study (Visit 3, treatment A) one tablet of 600 mg rifampicin will be given once daily on Days -6 to Day -1. One tablet of 25 mg BI 425809 will be given as a single dose approximately 10 h before the rifampicin administration on Day 1 (corresponding to the seventh day of the 10-day rifampicin treatment). Rifampicin will be continued for further 3 days (trial days 2, 3 and 4).

An overview of all relevant trial activities is provided in the [Flow Chart](#). For visit schedule and details of trial procedures at selected visits, refer to [Sections 6.1](#) and [6.2](#), respectively.

3.1.1 Administrative structure of the trial

The trial is sponsored by Boehringer Ingelheim (BI) Pharma GmbH & Co. KG, Germany.

BI has appointed a trial clinical monitor, responsible for coordinating all required activities, in order to

- manage the trial in accordance with applicable regulations and internal SOPs,
- direct the clinical trial team in the preparation, conduct, and reporting of the trial,
- ensure appropriate training and information of local clinical monitors, clinical research associates, and participating trial sites.

[REDACTED]

[REDACTED]

[REDACTED]

[REDACTED]

On-site monitoring will be performed by BI or a contract research organisation appointed by BI.

Data management and statistical evaluation will be done by BI according to BI SOPs.

Tasks and functions assigned in order to organise, manage, and evaluate the trial are defined according to BI SOPs. A list of responsible persons and relevant local information can be found in the investigator site file (ISF).

3.2 DISCUSSION OF TRIAL DESIGN, INCLUDING THE CHOICE OF CONTROL GROUPS

The study will be performed as a randomized, open-label, two period, fixed-sequence trial in healthy male subjects. This study design is considered to be appropriate to investigate the effect of multiple doses of rifampicin on single-dose PK of BI 425809 and to characterise the PK of its major metabolites.

Full induction effect of rifampicin can be expected after 1 week. The baseline activity after discontinuing rifampicin treatment can be attained within 2 weeks [[P03-08008](#)].

Due to the expected long half-life of metabolite BI 761036 a fixed sequence design was selected, with administration of rifampicin in the second study period only. The fixed-sequence design is not expected to lead to systematic errors in the estimation of the treatment effects, because the trial duration is short enough so that nonspecific time-effects are not expected.

The open-label treatment is not expected to bias results, since the study endpoints are derived from measurement of plasma concentrations of the analyte provided by a bioanalytical laboratory.

3.3 SELECTION OF TRIAL POPULATION

It is planned that 16 healthy male subjects will enter the study. They will be recruited from the volunteers' pool of the trial site.

Proprietary confidential information © 2017 Boehringer Ingelheim International GmbH or one or more of its affiliated companies

Rifampicin must not be used during pregnancy; furthermore oral contraceptives may become ineffective when co-administered with rifampicin. Therefore, the sponsor decided to only include male subjects into the study.

A log of all subjects enrolled into the trial (i.e. having given informed consent) will be maintained in the ISF at the investigational site irrespective of whether they have been treated with investigational drug or not.

3.3.1 Main diagnosis for study entry

The study will be performed in healthy subjects.

3.3.2 Inclusion criteria

Subjects will only be included into the trial, if they meet the following criteria:

1. Healthy male subjects according to the assessment of the investigator, based on a complete medical history including a physical examination, vital signs (BP, PR), 12-lead ECG, and clinical laboratory tests
2. Age of 18 to 55 years (incl.)
3. BMI of 18.5 to 29.9 kg/m² (incl.)
4. Signed and dated written informed consent prior to admission to the study in accordance with GCP and local legislation

3.3.3 Exclusion criteria

Subjects will not be allowed to participate if any of the following general criteria apply:

1. Any finding in the medical examination (including BP, PR or ECG) is deviating from normal and judged as clinically relevant by the investigator
2. Repeated measurement of systolic blood pressure outside the range of 90 to 140 mmHg, diastolic blood pressure outside the range of 50 to 90 mmHg, or pulse rate outside the range of 50 to 90 bpm
3. Any laboratory value outside the reference range that the investigator considers to be of clinical relevance
4. Any evidence of a concomitant disease judged as clinically relevant by the investigator
5. Gastrointestinal, hepatic, renal, respiratory, cardiovascular, metabolic, immunological or hormonal disorders
6. Cholecystectomy and/or surgery of the gastrointestinal tract that could interfere with the pharmacokinetics of the trial medication (except appendectomy and simple hernia repair)

Proprietary confidential information © 2017 Boehringer Ingelheim International GmbH or one or more of its affiliated companies

7. Diseases of the central nervous system (including but not limited to any kind of seizures or stroke), and other relevant neurological or psychiatric disorders
8. History of relevant orthostatic hypotension, fainting spells, or blackouts
9. Chronic or relevant acute infections
10. History of relevant allergy or hypersensitivity (including allergy to the trial medication or its excipients)
11. Use of drugs within 30 days prior to administration of trial medication if that might reasonably influence the results of the trial (incl. QT/QTc interval prolongation)
12. Participation in another trial where an investigational drug has been administered within 60 days prior to planned administration of trial medication, or current participation in another trial involving administration of investigational drug
13. Smoker (more than 10 cigarettes or 3 cigars or 3 pipes per day)
14. Inability to refrain from smoking on specified trial days
15. Alcohol abuse (consumption of more than 20 g per day)
16. Drug abuse or positive drug screening
17. Blood donation of more than 100 mL within 30 days prior to administration of trial medication or intended donation during the trial
18. Intention to perform excessive physical activities within one week prior to administration of trial medication or during the trial
19. Inability to comply with dietary regimen of trial site
20. Subject is assessed as unsuitable for inclusion by the investigator, for instance, because considered not able to understand and comply with study requirements, or has a condition that would not allow safe participation in the study

In addition, the following trial-specific exclusion criteria apply:

21. History of relevant liver diseases such as disturbance of liver function, jaundice, drug induced liver injury, Dubin-Johnson syndrome, Rotor syndrome, or liver tumours
22. Thrombocytes below lower limit of normal or liver enzymes (ALT, AST, GGT, AP) above upper limit of normal at the screening examination

For study restrictions, refer to [Section 4.2.2](#).

3.3.4 Removal of subjects from therapy or assessments

3.3.4.1 Removal of individual subjects

An individual subject is to be removed from the trial if:

1. The subject withdraws consent for trial treatment or trial participation, without the need to justify the decision
2. The subject needs to take concomitant drugs that interfere with the investigational product or other trial medication
3. The subject is no longer able to participate for other medical reasons (such as surgery, adverse events, or diseases)
4. The subject shows an elevation of AST and/or ALT ≥ 3 -fold ULN combined with an elevation of total bilirubin ≥ 2 -fold ULN (measured in the same blood sample) and/or needs to be followed up according to the 'DILI checklist' provided in the ISF.
5. The subject presents with a clinically relevant thrombocytopenia

A subject can also be removed from the trial if eligibility criteria are being violated or if the subject fails to comply with the protocol (for instance, by non-adherence to dietary rules, or non-attendance at study assessments).

If a subject is removed from or withdraws from the trial prior to first administration of trial medication, the data of this subject will not be entered in the case report form (CRF) or trial database and will not be reported in the clinical trial report (CTR). If a subject is removed from or withdraws from the trial after first administration of trial medication, this will be documented and the reason for discontinuation must be recorded in the CRF. In this case, the data will be included in the CRF/trial database and will be reported in the CTR. At the time of discontinuation a complete end of trial examination will be performed if possible and the information will be recorded in the CRFs. If the discontinuation occurs before the end of the REP (see [Section 5.2.2.2](#)), the discontinued subject should if possible be questioned for AEs and concomitant therapies at or after the end of the REP in order to ascertain collection of AEs and concomitant therapies throughout the REP, if not contrary to any consent withdrawal of the subject. These discontinuations will be discussed in the CTR.

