5.2.2.2 Adverse event collection and reporting

AEs collection

Upon enrolment into a trial, the subject's baseline condition is assessed (for instance, by documentation of medical history/concomitant diagnoses), and relevant changes from baseline are noted subsequently.

Subjects will be required to report spontaneously any AEs as well as the time of onset, end, and intensity of these events. In addition, each subject will be regularly assessed by the medical staff throughout the clinical trial and whenever the investigator deems necessary. As a minimum, subjects will be questioned for AEs (and concomitant therapies) at the time points indicated in the [Flow Chart](#). Assessment will be made using non-specific questions such as 'How do you feel?'. Specific questions will be asked wherever necessary in order to more precisely describe an AE.

[figure not shown]
A careful written record of all AEs shall be kept by the investigator in charge of the trial. Records of AEs shall include data on the time of onset, end time, and intensity of the event as well as any treatment or action required for the event and its outcome.

The following must be collected and documented on the appropriate CRF(s) by the investigator:

- From signing the informed consent onwards through the residual effect period (REP), until an individual subject's end of trial:
 - All AEs (serious and non-serious) and all AESIs.
 - The only exception to this rule are AEs (serious and non-serious) and AESIs in Phase I trials in healthy volunteers, when subjects discontinue from the trial due to screening failures prior to administration of any trial medication. In these cases, the subjects' data must be collected at trial site but will not be entered in the CRF or trial database and will not be reported in the CTR.

Proprietary confidential information © 2017 Boehringer Ingelheim International GmbH or one or more of its affiliated companies

- After the individual subject's end of trial:
 - The investigator does not need to actively monitor the subject for AEs but should only report relevant SAEs and relevant AESIs of which he may become aware of.

The REP for BI 425809, when measurable drug levels or pharmacodynamic effects are still likely to be present, is defined as 11 days after the last administration of BI 425809.

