6.2.3 End of trial period

For AE assessment, laboratory tests, recording of ECG and vital signs, and physical examination during the end of trial period, see [Sections 5.2.2](#) to 5.2.5.

Subjects who discontinue treatment before the end of the planned treatment period should undergo the end of trial visit.

All abnormal values (including laboratory parameters) that are judged clinically relevant by the investigator will be monitored using the appropriate tests until a return to a medically acceptable level is achieved. (S)AEs persisting after subject's end of trial must be followed up until they have resolved, have been sufficiently characterised, or no further information can be obtained.

The end of the trial as a whole is defined by the 'last regular visit completed by last subject' or 'end date of the last open AE' or 'date of the last follow-up test' or 'date of an AE has been decided as sufficiently followed-up', whichever is latest.

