5.2.2 Other Secondary endpoints

Secondary PK endpoints will be defined as in Section 5.5.1.2 of the CTP:

- $AUC_{0-\infty}$ of BI 425809 in plasma with and without co-administration of rifampicin (area under the concentration-time curve of the analyte in plasma over the time interval from 0 extrapolated to infinity)
- $t_{1/2}$ of BI 761036 in plasma without co-administration of rifampicin (terminal half-life of the analyte in plasma)

[figure not shown]

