6.7 BASELINE, TIME WINDOWS AND CALCULATED VISITS

Baseline for the evaluation of data of the “BI 425809+RI” treatment period will be defined as the last available value at Visit 3 before the second BI 425809 dose.

For an additional laboratory summary, baseline of treatment period 2 (“Loading RI” plus “BI 425809+RI”) is defined as the last follow-up assessment during treatment period 1 (i.e., lab value at Day 43).

Time windows are defined in Section 6.1 of the CTP. Adherence to time windows will be checked at the RPM/DBLM.

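### Withdrawing consent for trial treatment alone requires removal from the trial, and the follow-up then provided has no PK sample, so the remaining scheduled samples for a BI 425809 dose already taken would normally be lost even from a willing subject

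*Protocol*

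**What the plan says.** Protocol 3.3.4.1 lists conditions under which removal from the trial is mandatory. Its first is: "The subject withdraws consent for trial treatment or trial participation, without the need to justify the decision". The later sentence on eligibility violations and non-compliance makes removal only optional.

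For a subject removed after first dosing, the same section states: "At the time of discontinuation a complete end of trial examination will be performed if possible". It adds questioning on adverse events and concomitant therapies at or after the end of the residual effect period (REP), "if not contrary to any consent withdrawal of the subject". Protocol 6.2.3 is to the same effect: "Subjects who discontinue treatment before the end of the planned treatment period should undergo the end of trial visit".

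Flow Chart footnote 4 gives the content of that visit: "End of trial examination includes physical examination, vital signs, ECG, safety laboratory, recording of AEs and concomitant therapies". No PK sample is listed. Protocol 5.2.2.2 says the REP "is defined as 11 days after the last administration of BI 425809".

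PK sampling in the Flow Chart runs to 1008 h (Day 43) in Period 1 and to 168 h (Day 8) in Period 2. SAP 5.2.2 takes the secondary half-life endpoint from the reference period only: "of BI 761036 in plasma without co-administration of rifampicin".

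**The concern.** The heading of Protocol 3.3.4 names therapy and assessments as two things, but its rules offer one outcome, which is to leave the trial. BI 425809 is a single dose, so once the tablet is taken the profile can be completed without any further BI 425809. A subject may refuse more medication and still be willing to give blood. The section allows for partial consent in adverse event questioning but not in PK sampling, although PK is the purpose of the trial.

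Two situations matter:

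- **Period 1.** A subject decides before Day 43 that he will not take rifampicin. His own BI 761036 half-life cannot be obtained later, because it is defined only without rifampicin. Protocol 3.2 expects that half-life to be long, so late samples carry weight.
- **Period 2.** A subject takes BI 425809 on Day 1 and then refuses one of the four rifampicin doses still due. His 168 h sample, which closes the primary AUC0-168, falls after removal. The report planning meeting (RPM) may then have no complete value to judge.

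**Working it through.** The plan states no figure on this point. The check is a reading of the text, a count of samples, and a calculation of what a lost value would cost.

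**1. Is sampling after removal provided for elsewhere?** Protocol 5.5.2, 6.1, 6.2.2, 7.3, 7.3.5 and 7.4, and SAP 6.3 and 6.6, contain no rule for continuing PK sampling after treatment stops. SAP 6.6 reports the data that exist from subjects who do not complete; it does not provide for collecting more. The analysis could use such data, since the PK analysis set keeps a subject with one endpoint value from one period (Protocol 7.3).

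**2. Period 1 visits forgone (Flow Chart).** After 168 h: 216, 264, 336, 408, 504, 576, 672, 744, 840 and 1008 h, which is 10 visits. The REP is 11 × 24 = 264 h, and 8 of the 10 visits lie after it. Removal after 504 h forgoes 5 visits; after 840 h, 1.

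The analyte at each visit is uncertain because the table columns are broken. The rows from 216 to 504 h show at least two marks besides the adverse event mark, and those from 576 to 840 h show one. The row at 1008 h shows two, one probably the safety laboratory, since SAP 6.7 uses the "last follow-up assessment during treatment period 1 (i.e., lab value at Day 43" as a baseline. If the single late mark is the metabolite sample, AUC0-∞ of BI 425809 is at risk mainly from removal before about 504 h. The count of 10 visits does not depend on this reading.

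**3. Period 2 samples forgone (Flow Chart).** Footnote 3 puts rifampicin last at 10 h and 34 h, so those samples are taken first.

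| Rifampicin refused at | BI 425809 samples remaining | Number |
|---|---|---|
| 10 h | 12, 24, 34, 48, 72, 96, 168 h | 7 |
| 34 h | 48, 72, 96, 168 h | 4 |
| 58 h | 72, 96, 168 h | 3 |
| 82 h | 96, 168 h | 2 |

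**4. Ceiling on the precision loss.** Take the Protocol 7.1.3 model (random subject, fixed treatment), 16 subjects, m of them with a reference value only, and n = 16 − m complete pairs. Let L be the between-subject to within-subject variance ratio. Generalised least squares gives, relative to 16 complete pairs,

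variance ratio = 1 + (m / 2n) × (1 + 2L) / (1 + L).

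For example, m = 1 and L = 1 gives 1 + (1/30)(3/2) = 1.05, so the SE ratio is √1.05 = 1.0247. As L grows without limit the SE ratio tends to √(16/n), the same as losing the whole pair.

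The CI half-width ratio multiplies this by the ratio of t quantiles, with degrees of freedom taken as pairs minus 1: 1.7613/1.7531 for one lost value and 1.7709/1.7531 for two.

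| L | SE, 1 lost | Half-width, 1 lost | SE, 2 lost | Half-width, 2 lost |
|---|---|---|---|---|
| 0.5 | +2.2% | +2.7% | +4.7% | +5.7% |
| 1 | +2.5% | +3.0% | +5.2% | +6.3% |
| 4 | +3.0% | +3.4% | +6.2% | +7.3% |
| bound | +3.3% | +3.8% | +6.9% | +8.0% |

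**5. Half-life summary.** Protocol 7.3.5 requires at least 2/3 of the values: 16 × 2/3 = 10.67, so 11. The summary is suppressed only if 6 or more of 16 are missing.

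**The case against.** **Nothing forbids the samples.** A reader might infer that the protocol bars PK sampling after removal. No readable text says so, and redacted blocks follow Section 3.3.4.2. But this is more than silence: removal is mandatory, and the follow-up that replaces the schedule is listed without PK. A site following the text would normally stop sampling.

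**Period 1 offers no dose to refuse.** The only medication is one tablet on Day 1. The loss needs a subject who announces early that he will decline Period 2, is willing to keep giving blood, and is removed at once. That makes the case narrow, and it stands as a limit on frequency.

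**The Period 2 loss may not be due to this clause.** A subject who stops rifampicin has not had the full test treatment. Protocol 7.3 names an incorrect dose as a possible relevant violation, and SAP Table 6.2: 1 lists incorrect dose and non-compliance. The RPM might exclude his AUC0-168 with every sample in hand. This stands, and it makes the interval figures ceilings. It does not make the samples worthless: a subject who refuses only the 82 h dose has taken 9 of 10 doses, and the RPM cannot assess a profile that was never completed.

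**It changes no decision.** Protocol 7.2 sets no acceptance range and tests no hypothesis, and SAP 7.5.2 treats the half-life descriptively. This also stands and keeps the point minor.

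**Conclusion.** The gap is real and small. A mandatory rule treats refusal of further medication as departure from the trial, and the follow-up provided would normally end PK sampling for a BI 425809 dose already taken. Up to 10 visits after 168 h are at stake in Period 1, and 2 to 7 samples in Period 2.

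A reader might infer that the primary comparison stands to lose 3.8% to 8.0% of its precision. The documents do not support that. Those are upper bounds for one or two lost test values, and they apply only if the RPM would otherwise have accepted them. Nor is the half-life endpoint as a whole in danger, since its summary survives five missing values. By the 10 h rifampicin dose the early samples are already taken, so Cmax in Period 2 is probably unaffected.

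The figures rest on assumptions: one or two affected subjects, variance ratios of 0.5 to 4, and degrees of freedom equal to pairs minus 1. The documents give no rate of such withdrawals and no variance ratio. Whether AUC0-168 can be derived without the 168 h sample depends on a sponsor procedure that is not shown.

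**What to change.** In Protocol 3.3.4.1, with 6.2.3 aligned, separate (a) no further trial medication from (b) withdrawal from the trial. Under (a), if the subject consents and there is no medical objection, complete the remaining scheduled PK samples and adverse event questioning of the current period, then hold the end-of-trial examination. Leave the criteria for stopping medication unchanged, leave evaluability with the RPM under the existing rules, and leave the right to withdraw fully under (b) untouched.

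The costs are:

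- protocol and consent wording, with the approvals that Protocol 8.1 requires for amendments;
- attendance by the few willing subjects at visits already scheduled, at most 10 after 168 h in Period 1, while in Period 2 the last sample (168 h) comes before the adverse event contact already requested at or after 264 h;
- the alcohol and dietary restrictions of Protocol 4.2.2.2, which would continue until that subject's last PK sample and should be stated in the consent.
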